## **4. STUDY DESIGN AND PLAN**

This is a Phase 2, double-blind, randomized, placebo-controlled, multicenter study, evaluating the effects of OCA, and the subsequent addition of statin therapy, on lipoprotein metabolism in subjects with NASH with fibrosis stage 1 to 4, but no evidence of hepatic decompensation, in the DB phase, followed by an open-label LTSE phase to evaluate long term safety and efficacy.

Approximately 80 subjects with histological evidence of definite or probable NASH, who meet all inclusion and none of the exclusion criteria will be enrolled in the study. The histological evidence of definite or probable NASH will be based on the central read of a liver biopsy obtained no more than 1 year prior to randomization and a nonalcoholic fatty liver disease activity score (NAS) of 4 or greater. Subjects not using statin therapy (ie, statin-free) and statin-treated subjects may be enrolled. Statin-treated subjects will be required to stop statin treatment (after signing informed consent) for up to 5 weeks, including a 4-week statin washout period, prior to Randomization/Day 1.

Subjects will have a screening period of up to 5 weeks prior to Randomization/Day 1. At the Randomization (Day 1) Visit, subjects will be randomized in a 1:1:1:1 ratio to receive OCA 5 mg, OCA 10 mg, OCA 25 mg, or placebo, orally, once daily, for 16 weeks. Randomization will be stratified by the pre-randomization fasting serum LDLc ( $\leq$ 125 mg/dL or  $>$ 125 mg/dL) and baseline fibrosis stage (stage 1, 2 or stage 3, 4).

[figure not shown]
Subjects will attend on-site clinic visits at Weeks 2, 4, 8, 12, and 16 and will be contacted at Weeks 6, 10 and 14 to assess safety and treatment compliance. At the Week 4 Visit, all subjects will initiate treatment with atorvastatin at a dose of 10 mg once daily. At the Week 8 Visit, atorvastatin will be increased to 20 mg once daily (if 10 mg daily is tolerated), and continued for an additional 4 weeks. After 4 weeks of treatment at 20 mg, the atorvastatin dose may be titrated (up or down) as clinically indicated. The final visit during the DB phase will occur at Week 16, after which subjects may continue into the open-label LTSE.

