## **6.3. Data Handling**

### **6.3.1. Baseline Values**

Baseline values are defined as the last value (using fasting blood sample values for lipoprotein and plasma glucose) prior to administration of investigational product on Day 1 (predose).

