## 11.2. Adverse Events (AEs)

AE data will be collected from the time that signed informed consent is obtained until the subject fully completes her/his study participation of the study.

Pre-treatment AEs and treatment-emergent adverse events (TEAEs) will be summarized. TEAEs are defined as any AEs that newly appear, increase in frequency, or worsen in severity following initiation of investigational product. If it cannot be determined whether the AE is Treatment-Emergent due to a partial onset date, then it will be counted as treatment-emergent. Verbatim terms on eCRFs will be mapped to preferred terms and system organ classes using MedDRA (version 18.1).

Summaries that are displayed by system organ class and preferred terms will be ordered by descending order of incidence, for all OCA-treated patients, of system organ class and by preferred terms within each system organ class. Summaries of the following types will be presented by treatment group:

- Overall summary of TEAEs
- Subject incidence of pre-treatment AEs and the total number of entries by MedDRA system organ class and preferred term
- Subject incidence of TEAEs and the total number of entries by MedDRA system organ class and preferred term
- Subject incidence of drug-related TEAEs by MedDRA system organ class and preferred term. Related AEs are those with relationships reported as “Definite,” “Probable,” “Possible,” or with a missing relationship. This analysis will be performed for relationship to investigational product and to atorvastatin.
- Subject incidence of liver biopsy-related TEAEs by MedDRA system organ class and preferred term. Related AEs are those with relationships reported as “Definite” or AEs with a missing relationship.
- Subject incidence of serious TEAEs by MedDRA system organ class and preferred term

- Subject incidence of TEAEs leading to investigational product withdrawal by MedDRA system organ class and preferred term
- Subject incidence of TEAEs leading to study medication withdrawal by MedDRA system organ class and preferred term
- Subject incidence of TEAEs leading to study discontinuation by MedDRA system organ class and preferred term
- Subject incidence of TEAEs leading the investigational product withdrawal, study medication withdrawal, or study discontinuation by MedDRA system organ class and preferred term

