14.2.18.2	ITT	Summary of Bile Acids and Bile Acid Sub-components
14.2.18.3	ITT	Summary of Bile Acid Proportions
14.3		Safety Data
14.3.1	Safety	Summary of Investigational Product Exposure
14.3.2	Safety	Summary of Atorvastatin Exposure
14.3.3.1	Safety	Summary of Prior and New Concomitant Medications
14.3.3.2	Safety	Summary of New Concomitant Medications
14.3.1		Displays of Adverse Events
14.3.1.1.1	Safety	Overall Summary of Treatment-Emergent Adverse Events
14.3.1.1.2	Safety	Overall Summary of Treatment-Emergent Adverse Events Up to Week 4
14.3.1.2.1	Safety	Summary of Treatment-Emergent Adverse Events by System Organ Class and Preferred Term
14.3.1.2.2	Safety	Summary of Treatment-Emergent Adverse Events by Preferred Term
14.3.1.2.3	Safety	Summary of Treatment-Emergent Adverse Events Up to Week 4 by System Organ Class and Preferred Term
14.3.1.2.4	Safety	Summary of Treatment-Emergent Adverse Events Up to Week 4 by Preferred Term
14.3.1.3.1	Safety	Summary of Investigational product-related Treatment-Emergent Adverse Events by System Organ Class and Preferred Term
14.3.1.3.2	Safety	Summary of Investigational product-related Treatment-Emergent Adverse Events by Preferred Term
14.3.1.3.3	Safety	Summary of Investigational product-related Treatment-Emergent Adverse Events Up to Week 4 by System Organ Class and Preferred Term
14.3.1.3.4	Safety	Summary of Investigational product-related Treatment-Emergent Adverse Events Up to Week 4 by Preferred Term
14.3.1.4.1	Safety	Summary of Study Medication-related Treatment-Emergent Adverse Events by System Organ Class and Preferred Term
14.3.1.4.2	Safety	Summary of Study Medication-related Treatment-Emergent Adverse Events by Preferred Term
14.3.1.5.1	Safety	Summary of Liver biopsy-related Treatment-Emergent Adverse Events by System Organ Class and Preferred Term
14.3.1.5.2	Safety	Summary of Liver biopsy-related Treatment-Emergent Adverse Events by Preferred Term
14.3.1.6.1	Safety	Summary of Treatment-Emergent Serious Adverse Events by System Organ Class and Preferred Term
14.3.1.6.2	Safety	Summary of Treatment-Emergent Serious Adverse Events by Preferred Term
14.3.1.6.3	Safety	Summary of Treatment-Emergent Serious Adverse Events Up to Week 4 by System Organ Class and Preferred Term

Table Number	Population	Table Title
14.3.1.6.4	Safety	Summary of Treatment-Emergent Serious Adverse Events Up to Week 4 by Preferred Term

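### Biopsy-related adverse events are summarised among TEAEs only, although the one biopsy the SAP describes is taken before the first dose

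*SAP*

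**What the plan says.** Eligibility rests on the "central read of a liver biopsy obtained no more than 1 year prior to randomization" (SAP Section 4). Dosing starts on Day 1, the randomization visit, after screening: "Subjects will have a screening period of up to 5 weeks prior to Randomization/Day 1".

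Section 11.2 sets the collection period, "AE data will be collected from the time that signed informed consent is obtained", and the definition, "TEAEs are defined as any AEs that newly appear, increase in frequency, or worsen in severity following initiation of investigational product". An event whose status cannot be settled because of a partial onset date is counted as treatment-emergent.

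Among the planned summaries is "Subject incidence of liver biopsy-related TEAEs by MedDRA system organ class and preferred term". Appendix A carries this into Table 14.3.1.5.1, "Summary of Liver biopsy-related Treatment-Emergent Adverse Events by System Organ Class and Preferred Term", with 14.3.1.5.2 as its preferred-term counterpart. Biopsy-related means a relationship of *Definite* or a missing one. The preceding item in the same list defines drug-related as *Definite*, *Probable*, *Possible* or missing.

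Pre-treatment AEs and pre-treatment serious AEs have their own tables (14.3.1.12.1–2 and 14.3.1.13.1–2), with no split by relationship to biopsy. Listing 16.2.7.6 covers biopsy-related adverse events and, by its title, is not confined to treatment-emergent ones.

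**The concern.** A procedural complication usually follows the procedure. If the procedure comes before the first dose, so do most of its complications, and a filter that starts at first dose removes them. The SAP applies that filter to the one incidence summary that attributes events to the biopsy. The pre-treatment tables keep the events but not the attribution.

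The relatedness rule adds a second oddity. An event for which the investigator recorded no judgement would count as biopsy-related, while one judged probably related would not.

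At stake is the reading of two safety tables in the study report. Someone who turns to the table labelled biopsy-related may take a low count as evidence that the biopsy caused little harm, when the count reflects the filter.

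**Working it through.** No figure in the plan bears on this and no arithmetic applies. The check follows an event through the SAP's own definitions.

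**Inputs**
- Biopsy: up to 1 year before randomization (Section 4).
- AE collection: from signed consent (Section 11.2); screening lasts up to 5 weeks before Day 1 (Section 4).
- First dose: Day 1 (Sections 4 and 6.3.1).
- TEAE: new, more frequent or worse after first dose; undeterminable partial dates count as TEAE (Section 11.2).
- Safety Population: subjects who received any investigational product (Section 7.3).
- Other biopsies in the double-blind phase: none described. On-treatment fibrosis is followed by transient elastography and laboratory-based scores (Sections 3.3.3, 3.3.8, 9.3.4 and 9.3.5). Biopsy enters only as a baseline stage.

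**Where a biopsy event ends up**

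| Onset | Class | Biopsy-related Tables 14.3.1.5.1–2 | Elsewhere |
|---|---|---|---|
| Before consent | Outside AE collection | No | Not collected as an AE |
| Consent to first dose, full date, no later worsening | Pre-treatment AE | No | 14.3.1.12 (and 14.3.1.13 if serious), unattributed; Listing 16.2.7.6 by its title |
| Consent to first dose, worse or more frequent after dosing | TEAE | Yes, if *Definite* or missing | TEAE tables |
| Partial date, status undeterminable | Counted as TEAE | Yes, if *Definite* or missing | TEAE tables |
| After first dose | TEAE | Yes, if *Definite* or missing | TEAE tables |

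The second row is the ordinary course for a complication of a screening biopsy, and it is the row that the biopsy tables exclude.

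**Relatedness rules side by side (Section 11.2)**

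| Recorded relationship | Drug-related | Biopsy-related |
|---|---|---|
| *Definite* | Yes | Yes |
| *Probable* | Yes | No |
| *Possible* | Yes | No |
| Missing | Yes | Yes |

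The middle two rows matter only if the eCRF records the biopsy relationship on the same scale as the drug relationship. The SAP does not state the biopsy scale.

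**The case against.** The strongest reply is that the table does what it says. The safety endpoint in Section 3.2.3 is TEAE incidence, the summary is of biopsy-related TEAEs, and the SAP nowhere says that it is meant to display harms of the qualifying biopsy. That is fair about stated purpose. It does not explain why a summary by biopsy relationship should begin after the only biopsy described.

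A second reply is that the protocol, which is not at hand, may schedule a biopsy in the double-blind phase, or that one may be done unscheduled; Section 11.5 collects on-study procedures. Either would give the TEAE table something to catch. It would not bring back screening-period events, and nothing in the SAP points to a scheduled on-treatment biopsy.

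A third reply is that the events remain visible. This stands. A reader might infer that biopsy harm would disappear from the report. The documents do not support that: the pre-treatment tables give incidence by system organ class and preferred term, and Listing 16.2.7.6 should show the attribution. With about 80 subjects, a listing of a few events is readable. What is missing is the attributed incidence summary.

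A reader might also infer that the biopsy tables would be empty, or filled mainly with unrelated on-treatment events whose biopsy field was left blank. Neither follows. Worsening, delayed and partial-date events can enter, and the SAP gives no missingness rate from which to judge how many blanks there would be. Counting a missing relationship as related is also the convention that the SAP uses for drug relatedness.

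**Conclusion.** The mismatch is real and limited. As written, an event with onset between consent and first dose is left out of the only incidence summary by biopsy relationship, unless it worsens or becomes more frequent after dosing or has an undeterminable partial onset date. Two descriptive tables are affected, in Section 11.2 and Appendix A. No efficacy result, error rate or comparison between arms changes.

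This rests on one assumption: that the protocol adds no scheduled biopsy in the double-blind phase. If it does, the tables have a clearer use, though screening-period events would still be excluded.

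The difference in relatedness grades is a secondary point and is conditional. If the biopsy relationship is recorded on the drug scale, the rule excludes events judged probable or possible while including events with no judgement, and the SAP gives no reason. If the biopsy scale has other categories, that part falls away.

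**What to change.** In Section 11.2, base the biopsy-related summary on all AEs collected from informed consent, or keep the TEAE summary and add a pre-treatment biopsy-related table. Change Tables 14.3.1.5.1 and 14.3.1.5.2 in Appendix A to match. If the biopsy relationship uses the same eCRF scale as the drug relationship, count the same grades or state why they differ. Showing missing relationships in a separate row would help the reader but is optional.

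The table should carry a note on its reach: it covers events with onset from consent onward in dosed subjects. Events that began before consent, and events in subjects who had a biopsy but were never dosed, stay outside it, so it is not a full incidence of biopsy harm.

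The cost is a wording change and a different filter for two tables, or one added table. No new data are needed.

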## 2. STUDY OBJECTIVES

The DB primary objective is to evaluate the effect of obeticholic acid (OCA) on low-density lipoprotein (LDL) metabolism in subjects with biopsy-confirmed nonalcoholic steatohepatitis (NASH) and to assess the ability of atorvastatin to modulate this effect.

The DB secondary objectives are:

- To evaluate the safety and tolerability of OCA alone and in combination with atorvastatin therapy in subjects with biopsy-confirmed NASH.
- To evaluate the effect of OCA with and without atorvastatin therapy, on
  - High-density lipoprotein (HDL), very low-density lipoprotein (VLDL), triglycerides (TG), total cholesterol, and apolipoprotein (Apo) concentrations
  - Components of the reverse cholesterol transport pathway

The DB exploratory objectives are:

- To evaluate the effect of OCA on:
  - Liver biochemistry, inflammation, and apoptosis
  - Markers of glucose metabolism including C-peptide, insulin, fasting plasma glucose, hemoglobin-specific A1c fraction (HbA1c), homeostatic model assessment – beta-cell function (HOMA- $\beta$ ), and homeostatic model assessment – insulin resistance (HOMA-IR)
  - Anthropometric measures including height (measured at Screening Visit 1 only), weight, waist and hip circumference measurements, body mass index (BMI), and waist-to-hip ratio calculations
  - Cardiovascular risk scores (eg, Framingham Risk Score [FRS] and Reynolds score)

- To evaluate the pharmacokinetics (PK) and pharmacodynamics (PD) of OCA and its conjugates
- To evaluate the bioanalytical concentrations of atorvastatin and its metabolites
- To evaluate improvement in noninvasive-radiological assessment of fibrosis via transient elastography (TE; at sites where available)

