- Subject incidence of TEAEs by MedDRA system organ class, preferred term, and maximum severity will be presented. At each level of subject summarization, a subject is classified according to the maximum severity if the subject reported one or more events. AEs with missing severity will be considered severe for this summary.

The summaries above will be repeated presenting only preferred term ordered by descending order of incidence, for all OCA treated subjects, excluding system organ class.

In addition, other than Follow-up TEAEs, these summaries will be repeated for the time period up to Week 4, to evaluate the effects of OCA alone and in combination with atorvastatin. These analyses will include TEAEs with date of onset prior to the start of atorvastatin.

The following listings will be presented by subject:

- All AEs
- Serious AEs (subset of the AEs where serious is marked as “Yes”)
- Death information will be provided in a separate listing, should any deaths occur
- AE’s leading to withdrawal of investigational product
- AEs leading to withdrawal of study medication
- AEs leading to Study Discontinuation

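### The adverse event incidence tables have no counterpart for the period on OCA plus atorvastatin: the period-specific set stops where atorvastatin starts

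*SAP*

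**What the plan says.** - **Objective.** SAP Section 2 lists as a secondary objective "To evaluate the safety and tolerability of OCA alone and in combination with atorvastatin therapy in subjects with biopsy-confirmed NASH".
- **Design.** Under Section 4, investigational product is taken "orally, once daily, for 16 weeks". On atorvastatin: "At the Week 4 Visit, all subjects will initiate treatment with atorvastatin at a dose of 10 mg once daily". This applies to every arm, placebo included.
- **What counts as an event.** Section 11.2: "TEAEs are defined as any AEs that newly appear, increase in frequency, or worsen in severity following initiation of investigational product". The main tables therefore run from the first dose of investigational product, with no division at the start of atorvastatin.
- **The period-specific tables.** Section 11.2 adds that the summaries will be "repeated for the time period up to Week 4, to evaluate the effects of OCA alone and in combination with atorvastatin". It then gives the inclusion rule: "These analyses will include TEAEs with date of onset prior to the start of atorvastatin".
- **Planned output.** Appendix A pairs whole-phase TEAE tables with versions such as Table 14.3.1.1.2, "Overall Summary of Treatment-Emergent Adverse Events Up to Week 4". No adverse event table is defined by onset on or after the first atorvastatin dose. The tables for pruritus, hepatic disorders, dyslipidaemia, myopathy and cardiovascular events have no Week 4 version at all.

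**The concern.** The purpose given for the repeated tables has two halves, OCA alone and OCA with atorvastatin. The inclusion rule serves only the first. Because atorvastatin starts at Week 4 in all arms, a table restricted to earlier onset cannot contain an event that arose on the combination.

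A reader who wants adverse event incidence on the combination would have to use the 16-week tables. These mix the two periods, and most of their planned time falls after Week 4. Subject incidence can only rise as follow-up lengthens, so the 16-week figure will usually exceed the Week 4 figure whether or not atorvastatin contributes anything. At stake is a wrong impression, in either direction, of what adding atorvastatin does to tolerability.

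**Working it through.** The SAP states no figure on this point, so there is none to reproduce. The check is a comparison of passages followed by an illustration.

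**1. Purpose against content.** The purpose sentence in Section 11.2 names both conditions; the inclusion sentence admits onset before atorvastatin only. With atorvastatin starting at Week 4 (Section 4), the repeated tables hold events from the first condition alone.

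**2. What Appendix A offers after Week 4.**
- Whole-phase TEAE tables, which include the first 4 weeks.
- TEAEs related to study medication (14.3.1.4.1 and 14.3.1.4.2) and TEAEs leading to its withdrawal (14.3.1.10.1 and 14.3.1.10.2). These select by attribution or action taken. An event on the combination that is attributed to OCA, or to neither drug, is not isolated.
- Time to first and to most severe onset for the events of special interest, and time to first onset for cardiovascular events.
- For pruritus only, event days per subject-year (Section 11.3.1), not split by period.

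**3. Planned exposure.** Before atorvastatin: 4 × 7 = 28 days. With atorvastatin: 12 × 7 = 84 days. Total: 112 days. The combination period is 84/112 = 75% of planned time and 84/28 = 3 times the earlier period. The 16-week table covers 112/28 = 4 times the time of the Week 4 table.

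**4. Illustration with no atorvastatin effect.** Assume a constant event rate, events in the two periods independent, and every subject followed for 16 weeks. With p the incidence by Week 4, incidence over 12 weeks is 1 − (1 − p)^3 and over 16 weeks 1 − (1 − p)^4.

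| Week 4 | 12 weeks on combination | 16-week total | Total minus Week 4 |
|---|---|---|---|
| 5% | 14.3% | 18.5% | 13.5% |
| 10% | 27.1% | 34.4% | 24.4% |
| 20% | 48.8% | 59.0% | 39.0% |
| 30% | 65.7% | 76.0% | 46.0% |

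The total is well above the Week 4 figure although atorvastatin does nothing. Subtracting one table from the other does not recover combination-period incidence either. A subject with the same event in both periods counts once in each table, so the last column falls short of the second.

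**5. Similar totals from opposite effects.** If the hazard changes by a factor r when atorvastatin starts, the 16-week incidence is 1 − (1 − p)^(1 + 3r).
- p = 10%, r = 2: 1 − 0.9^7 = 52%.
- p = 30%, r = 1/3: 1 − 0.7^2 = 51%.

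A doubled hazard and one cut to a third give nearly the same 16-week total. The two cases differ in the Week 4 table, but separating them requires a model that the SAP does not plan.

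**The case against.** **The objective has other support.** A reader might infer that the secondary safety objective cannot be answered from the planned output. The SAP does not support that. Laboratory values, vital signs and ECGs are summarised by scheduled visit (Sections 11.6 to 11.8), which separates visits up to Week 4 from later ones. The gap concerns adverse event incidence.

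**Combination-period events are not confined to the 16-week totals.** The atorvastatin-related and withdrawal tables mostly describe that period, although Section 11.2 also counts a missing relationship as related. For pruritus, Kaplan-Meier curves with numbers at risk allow onset before and after Week 4 to be read off. These outputs are real but partial: they cover selected events, or the first or most severe event.

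**The randomised comparison is intact.** All arms add atorvastatin at Week 4, so within each table OCA and placebo share the same planned period. Accumulation over time does not bias that comparison, and the percentages above matter only if someone sets the Week 4 table against the 16-week table within an arm. This stands. However, the stated purpose of the repeated tables invites exactly that contrast.

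**A kinder reading.** The Week 4 set shows OCA alone and the full set beside it shows the course with atorvastatin, so the sentence is merely loose. This does not close the gap, because the full set contains the first 4 weeks, gives no subject-time and cannot be differenced.

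**Weight.** The trial has about 20 subjects per arm, Section 6.2.8 treats results as descriptive, and every event is listed by subject. That limits the consequence. It also means that no new data are needed.

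**Conclusion.** The point holds for the adverse event incidence tables. Section 11.2 states a purpose that its own inclusion rule cannot meet, and Appendix A confirms that no incidence table isolates the period on OCA plus atorvastatin, which is 75% of planned treatment time.

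The 34%, 59% and 76% figures show how far apart the two existing tables would lie with no atorvastatin effect. They rest on an assumed constant hazard and complete follow-up, not on rates in the SAP. Actual exposure will differ from 28 and 84 days with dropout or a shifted atorvastatin start. The finding should be corrected, but it does not undermine the safety evaluation as a whole or the comparison of OCA with placebo.

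**What to change.** Amend Section 11.2 and Appendix A before database lock; tables added later would have to be labelled post hoc under Section 1.

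1. Keep the pre-atorvastatin tables and describe their purpose as OCA or placebo alone.
2. Add matching tables by treatment group for TEAEs with onset or worsening on or after the first atorvastatin dose, with subjects who took atorvastatin as denominator. Include the events of special interest.
3. State to which period an event is assigned when it begins before atorvastatin and worsens afterwards, since worsening counts as treatment-emergent.
4. Show subject-time, or exposure-adjusted rates, for both periods.
5. State that each period is to be read against placebo in the same period. A before/after contrast within an arm remains confounded with time on OCA, and the later denominator leaves out subjects who stopped before atorvastatin.

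The cost is a few more tables. Onset and dosing dates are already used elsewhere in the SAP, so no further data collection is needed.
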